10.6. Appendix 6: Derived and Transformed Data

10.6.1. General

| Multiple Measurements at One Time Point |
|---|
| 
 Mean of the measurements will be calculated and used in any derivation of summary statistics but if listed, all data will be presented. If there are two values within a time window the value closest to the target day for that window will be used. If values are the same distance from the target then the mean will be taken. Subjects having both High and Low values for Normal Ranges at any post-baseline visits for safety parameters will be counted in both the High and Low categories of “Any visit post-baseline” row of related summary tables. This will also be applicable to relevant Potential Clinical Importance summary tables. |
| Study Day |
| Calculated as the number of days from randomisation date : |
| 
 Ref Date = Missing → Study Day = Missing Ref Date < Start of treatment date → Study Day = Ref Date – Start of treatment date Ref Date ≥ Start of treatment date → Study Day = Ref Date – (Start of treatment date) + 1 |
| Date of Completion/Withdrawal |
| The date of completion/withdrawal will be derived as follows: 
 For subjects who complete the last on-treatment study visit, the date of completion/withdrawal will be the date of that visit (Visit 9). For subjects who withdraw from the study, the date of completion/withdrawal will be the latest of the date of the last attended scheduled clinic visit (excluding follow-up), the date of the EW visit (if present) and the last dose date. |

10.6.2. Study Population

| Demographics |
|--|
| Age |
| 
 Age will be calculated based on the Pre-screening visit date. GSK standard IDSL algorithms will be used for calculating age where birth date will be imputed as follows: 
 Any subject with a missing day will have this imputed as day ‘15’. Any subject with a missing date and month will have this imputed as ‘30th June’. Birth date will be presented in listings as ‘YYYY’. |
| Body Mass Index (BMI) |
| 
 Calculated as Weight (kg) / [Height (m)²] |

Smoking Status

At Screening, subjects who were identified as former smokers but who last smoked within 6 months prior to Screening will be re-classified as current smokers prior to summarizing. Subject listings will include original and re-classified status.

During the study, smoking status will be derived from smoking status at Screening and records of change in smoking status at visits. A subject identified as a current smoker at Screening who stopped smoking during the study will be assessed as a former smoker only at visits which are at least 6 months after the date the subject last smoked. Former smokers who started smoking will be considered current smokers at all visits after the date the subject started smoking.

In order to assess the last time a subject smoked the partial date will be imputed to earliest date within the month or year e.g. If a subject has only remembered the year they last smoked (----2010) then impute to 01JAN2010. If a subject has remembered the month and year that they last smoked (--SEP2010) then impute to 01SEP2010.

Concomitant Medications

COPD concomitant medications will be grouped into the following RMCs based on pre-defined code lists derived from ATC classifications:

Short-acting anticholinergic
Short-acting beta-2 agonist
Long-acting anticholinergic
Long-acting beta-2 agonist - Group 1
Long-acting beta-2 agonist - Group 2 (Olodaterol or Indacaterol)
Long-acting beta-2 agonist - Group 3 (Salmeterol and Formoterol)
Xanthine
PDE4 Inhibitors
Corticosteroid - Inhaled
Corticosteroid - Depot
Corticosteroid - Systemic, oral, parenteral and intra-articular
Corticosteroid - Other
Leukotriene Receptor Antagonist
Nedocromil or Cromolyn Sodium
Mucolytics
Cytochrome P450 3A4 Strong Inhibitors
Oxygen
Antiinfectives (antibiotics, antifungals, antivirals, antiseptics)
Other medication given for exacerbation
Other COPD medication
Other

COPD concomitant medications that were stopped more than 30 days prior to Screening and non COPD concomitant medications that were stopped prior to Screening will not be presented in any tables or listings.

For reporting purposes, the LABA groups will be combined in the concomitant medication tables.

Treatment Compliance

The number of doses of study treatment taken by each subject from each inhaler will be calculated from the dose counter start and stop counts for each inhaler used. If a dose counter start count is missing then it will be assumed to be 30. If all dose counter stop counts are non-missing then the percentage compliance will be calculated as:

$$\text{Compliance} = \frac{\text{sum of all (dose counter start} - \text{dose counter stop)}}{(\text{exposure stop date} - \text{exposure start date} + 1)} \times 100$$

If any dose counter stop is missing then the treatment compliance will be set to missing for that subject.

Overall compliance will be categorised as follows:

< 80 %
 $\geq 80\%$ to $< 95\%$
 $\geq 95\%$ to $\leq 105\%$
 $> 105\%$ to $\leq 120\%$
 $> 120\%$.

If a subject received a treatment other than the randomised treatment during the study, the compliance will still be calculated using data from all containers received and overall exposure start and stop dates.

10.6.3. Safety

Extent of Exposure

- Number of days of exposure to study drug will be calculated based on the formula:

$$\text{Duration of Exposure in Days} = \text{Overall Treatment Stop Date} - \text{Overall Treatment Start Date} + 1$$
- If there are any treatment breaks during the study, exposure data will be adjusted accordingly.
- If overall treatment stop date is missing it will be imputed as follows:
 - For subjects who attended a Study Treatment Discontinuation visit, use the date of the Study Treatment Discontinuation visit
 - For subjects who attended the last on-treatment visit, use the Visit 8 (Week 24) date.
 - For subjects who died and did not attend a Study Treatment Discontinuation visit or the last on-treatment visit, use the date of death
 - For all other subjects, use the last recorded exposure start or stop date.
- If a subject's overall exposure start date is missing then it will be assumed to be their Day 1 visit date.
- If a subject received a treatment other than the randomised treatment during the study, the exposure will still be calculated based on overall exposure start and stop dates.

Adverse Events

- The most frequent on-treatment AEs will be defined as the on-treatment AEs experienced by 3 % (after rounding) or more of subjects in any treatment group.
- AE groups of special interest have been defined as AEs which have specified areas of interest for UMEC. The following table presents the special interest AE groups and subgroups. The complete list, including the PTs which contribute to each of the groups will be provided by Global Clinical Safety and Pharmacovigilance (GCSP) using the MedDRA version current at the time of reporting. This will be finalized prior to unblinding.

| Special Interest AE Group | Special Interest AE Subgroup |
|--|--|
| Cardiovascular effects | Cardiac Arrhythmia Cardiac Failure Cardiac Ischaemia Hypertension Stroke |
| Urinary Retention | |
| Pneumonia | |
| Anticholinergic syndrome | |
| Gastrointestinal obstruction | |
| Hypersensitivity | |
| LRTI excluding pneumonia | |
| Ocular effects (antimuscarinic) | |
| Paradoxical bronchospasm | |
| gallbladder disorders | |
| 
 • A flag will be derived to identify on-treatment AEs of special interest. In order to ensure consistency with the umeclidinium Global ISS, all outputs will use the same MedDRA version (i.e. v 15.0) and the same list of special interest terms as was used for the umeclidinium Global ISS. | |
| 
 • The AESI category designated as Pneumonia and LRTI will include lower respiratory tract infections and related diseases. Also, the category designated as "Anticholinergic Syndrome" will be referenced as "Anticholinergic Effects" since the Anticholinergic Syndrome SMQ which was used to locate terms includes events that are often associated with anticholinergic or antimuscarinic medication, but are not necessarily diagnostic for anticholinergic syndrome. | |

Laboratory Parameters

- The baseline value for a parameter will be the most recent recorded value for that parameter before dosing on Day 1 at schedule visit.

Laboratory Parameters

- Laboratory data values will be classified as 'low', 'normal' or 'high' with reference to normal ranges.
- An 'any visit post-baseline' classification will be derived, in which subjects will be counted in the 'low' and 'high' categories if they reported a low or high value at any scheduled, unscheduled or EW visit made after the start of study treatment, up to a maximum of two weeks after the last dose of study treatment. Subjects who did not report a low or high value at any visit after the start of study treatment will be counted in the 'normal' category.
- Change from baseline values will be classified relative to the normal range as 'to low', 'to normal or no change' or 'to high'. Subjects who do not change categories or move from out-of-range to normal will be classified as 'to normal or no change'.
- An 'any visit post-baseline' change classification will be derived, in which subjects will be counted in the 'to low' and 'to high' categories if they reported a change from a 'normal' baseline to a value below or above the normal range (respectively) at any scheduled, unscheduled or EW visit made after the start of study treatment, up to a maximum of 2 weeks after the last dose of study treatment. Subjects who did not report a change to a value outside the normal range at any visit after the start of study treatment will be counted in the 'to normal or no change' category.
- If a laboratory value which is expected to have a numeric value for summary purposes, has a non-detectable level reported in the database, where the numeric value is missing, but typically a character value starting with '<x' or '>x' (or indicated as less than x or greater than x in the comment field) is present, the number of significant digits in the observed values will be used to determine how much to add or subtract in order to impute the corresponding numeric value.
 - Example 1: 2 Significant Digits = '< x' becomes x – 0.01
 - Example 2: 1 Significant Digit = '> x' becomes x + 0.1
 - Example 3: 0 Significant Digits = '< x' becomes x – 1

Vital Signs

- The baseline value for a vital sign endpoint will be the most recent recorded value for that endpoint before dosing on Day 1 at schedule visit.
- The 'maximum/minimum post-baseline' value will be the maximum value for pulse rate and systolic blood pressure, or the minimum value for diastolic blood pressure, recorded at any scheduled, unscheduled or EW visit made after the start of study treatment.

12-Lead ECG

- The baseline value for an ECG endpoint will be the most recent recorded value for that endpoint before dosing on Day 1 at schedule visit.
- A 'maximum post-baseline' QTc(F), QTc(B), PR interval and heart rate value will be derived as the maximum value recorded at any scheduled, unscheduled or EW visit made after the start of study treatment.
- QTc(F) values (including 'maximum post-baseline') will be categorised as follows:
 - ≤ 450 msec
 - > 450 to ≤ 480 msec
 - > 480 to ≤ 500 msec

12-Lead ECG

> 500 msec.

- Change from baseline QTc(F) values (including change to 'maximum post baseline') will be categorised as follows:
 - < -60 msec
 - ≥ -60 to < -30 msec
 - ≥ -30 to < 0 msec
 - ≥ 0 to < 30 msec
 - ≥ 30 to < 60 msec
 - ≥ 60 msec.
- An 'any time post-baseline' ECG interpretation will be derived as the worst interpretation recorded at a scheduled, unscheduled or EW visit made after the start of study treatment. The order of severity from worst to best for ECG interpretation is: abnormal: clinically significant, abnormal: not clinically significant, normal, unable to interpret.
- Any ECG abnormality recorded by a subject with an ECG interpretation of 'abnormal: clinically significant' after the start of study treatment will be included in an 'any-time post-baseline' record of ECG abnormalities.
- Any ECG abnormality recorded by a subject after the start of study treatment will be included in an 'any-time post-baseline' record of all ECG abnormalities.

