| 3.15. | 3.15 | Modified ITT | DB2114634 7.07 | Summary of Serious Adverse Events by System Organ Class | | SAC[1] |
| 3.16. | 3.16 | Modified ITT | DB2114634 7.07 | Summary of Drug-Related Serious Adverse Events by System Organ Class | | SAC |
| 3.17. | 3.17 | Modified ITT | DB2114634 7.13 | Summary of On-treatment Non-Fatal Serious Adverse Events | | SAC |
| 3.18. | 3.18 | Modified ITT | DB2114634 7.14 | Summary of Post-treatment Non- Fatal Serious Adverse Events | | SAC |
| 3.19. | 3.19 | Screen and Run-in Failure | DB2114634 7.15 | Summary of Pre-treatment Adverse Events Leading to Withdrawal from the Study | | SAC |

| Safety : Tables | | | | | | |
|-----------------|--------------------|--------------|-------------------------------|---|-------------------|------------------------|
| IMCT No. | China Subgroup No. | Population | IDSL / TST ID / Example Shell | Title | Programming Notes | Deliverable [Priority] |
| 3.20. | 3.20 | Modified ITT | DB2114634 7.16 | Summary of On-treatment Adverse Events Leading to Discontinuation of Study Treatment or Withdrawal from the Study | | SAC |
| 3.21. | 3.21 | Modified ITT | DB2114634 7.17 | Summary of On-treatment Adverse Events of Special Interest | | SAC[1] |
| 3.22. | 3.22 | Modified ITT | DB2114634 7.18 | Summary of Fatal Serious Adverse Events of Special Interest | | SAC |
| 3.23. | 3.23 | Modified ITT | DB2114634 7.19 | Summary of On-treatment Non-Fatal Serious Adverse Events of Special Interest | | SAC |
| 3.24. | 3.24 | Modified ITT | DB2114634 7.20 | Summary of Fatal Drug Related Serious Adverse Events | | SAC |
| 3.25. | 3.25 | Modified ITT | DB2114634 7.21 | Summary of On-treatment Non-Fatal Drug Related Serious Adverse Events | | SAC |
| 3.26. | 3.26 | Modified ITT | DB2114634 7.22 | Summary of Chemistry Data | | SAC |
| 3.27. | 3.27 | Modified ITT | DB2114634 7.23 | Summary of Change from Baseline in Chemistry Data | | SAC |
| 3.28. | 3.28 | Modified ITT | DB2114634 7.24 | Summary of Chemistry Data Outside the Normal Range | | SAC |
| 3.29. | 3.29 | Modified ITT | DB2114634 7.25 | Summary of Chemistry Changes from Baseline Relative to the Normal Range | | SAC |
| 3.30. | 3.30 | Modified ITT | DB2114634 7.26 | Summary of Haematology Data | | SAC |

| Safety : Tables | | | | | | |
|-----------------|--------------------|--------------|-------------------------------|---|-------------------|------------------------|

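### The any-visit laboratory shift row never counts low-to-high or high-to-low changes as shifts, although the by-visit rule in the same section does

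*SAP*

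**What the plan says.** SAP 10.6.3, Laboratory Parameters, defines two change classifications against the normal range. Both use the categories 'to low', 'to normal or no change' and 'to high'.

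- **By visit.** The middle category is closed: "Subjects who do not change categories or move from out-of-range to normal will be classified as" 'to normal or no change'. No condition is placed on the baseline category.
- **Any visit post-baseline.** To be 'to low' or 'to high', a subject must have moved from a 'normal' "baseline to a value below or above the normal range (respectively) at any scheduled, unscheduled or EW visit", after treatment started and no later than two weeks after the last dose. The residual rule is that "Subjects who did not report a change to a value outside the normal range at any visit after the start of study treatment" are placed in 'to normal or no change'.

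These rules feed Table 3.29, "Summary of Chemistry Changes from Baseline Relative to the Normal Range", and its haematology counterpart, Table 3.33 (SAP 10.14.8). Both are produced for the overall population and for China.

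Two other sections determine what the any-visit row has to carry. SAP 10.5.3 keeps unscheduled visits out of summary tables except in a worst-case post-baseline assessment. SAP 10.7.1 does the same for data from a standalone early withdrawal (EW) visit.

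**The concern.** The two rules disagree about a subject whose baseline is out of range on one side and who later has a value out of range on the other. The by-visit rule treats this as a shift. The any-visit rule does not, because the baseline was not normal.

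The any-visit row should be at least as inclusive as any single-visit row in the same table. As written it can be less so. It is also the only row of the shift table that can take unscheduled and standalone EW results. Protocol Table 5 schedules post-baseline chemistry and haematology only at Visits 6 and 8, plus the EW visit, so those extra results are a real part of what the row must capture. A programmer following the text would produce a safety count that contradicts the rest of the table, or would have to guess the intention.

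**Working it through.** The plan states no figure to reproduce, because this is a classification rule. The check is to apply both rules to every possible pattern.

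**Inputs (all SAP 10.6.3).**
1. By visit: 'to normal or no change' if the category is unchanged or the value returns to normal. Otherwise the subject is 'to low' or 'to high', according to the value.
2. Any visit: "subjects will be counted in the 'to low' and 'to high' categories if they reported a change from a 'normal' baseline" and then had a value outside the range.
3. Any-visit residual: no change to a value outside the range was reported. This has two readings. *Literal*: any such change disqualifies. *Complement*: only the change defined in the sentence before, from a normal baseline, disqualifies.

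**Enumeration.** There are 3 baseline categories and 2³ − 1 = 7 non-empty sets of post-baseline categories, so 3 × 7 = 21 patterns.

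| Baseline | Post-baseline categories seen | By visit | Any visit, literal | Any visit, complement |
|---|---|---|---|---|
| Low | {high}, {low, high}, {normal, high}, {low, normal, high} | 'to high' at each high visit | no category | 'to normal or no change' |
| High | {low}, {low, high}, {low, normal}, {low, normal, high} | 'to low' at each low visit | no category | 'to normal or no change' |
| Normal (7 patterns) | any | as observed | agrees | agrees |
| Low without any high (3), high without any low (3) | remaining sets | 'to normal or no change' | agrees | agrees |

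So 4 + 4 = 8 of the 21 patterns are affected, and 7 + 3 + 3 = 13 are classified consistently. In all 8, at least one by-visit result is a shift, and neither reading of the any-visit rule counts one. These are counts of patterns, not of subjects.

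**When the any-visit row falls below a visit row.** For one analyte and visit, let *a* be the number of normal-baseline subjects above range and *b* the number of low-baseline subjects above range. The visit row shows *a* + *b* as 'to high'. The any-visit row shows *A*, the number of normal-baseline subjects above range at any visit, with *A* ≥ *a*. The any-visit count is the smaller whenever *A* − *a* < *b*. The simplest case is one low-baseline subject who is high at Visit 6, with nobody else high at any time. The Visit 6 row shows 1 and the any-visit row shows 0.

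**Crossing seen only at an unscheduled or standalone EW visit.** SAP 10.5.3 and 10.7.1 keep the result out of the visit rows, and the any-visit rule does not count it as a shift. No row of Table 3.29 or 3.33 shows it as one.

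**Check of the fix.** With any-visit 'to high' requiring only a baseline that was not high, and 'to low' only a baseline that was not low, all 21 patterns receive a category. The 8 affected patterns move to the category that the by-visit rule gives, and the other 13 are unchanged.

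**The case against.** **The residual sentence can be read as the complement of the one before it.** Nobody then drops out of the row. This is a fair reading. A reader might infer that these subjects certainly have no category, but the text does not settle that. The complement reading replaces an omission with a misclassification, because a low-to-high subject is then labelled as returned to normal or unchanged. The contradiction with the by-visit rule remains.

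**SAP 10.6.1 may help.** It provides that "Subjects having both High and Low values for Normal Ranges at any post-baseline visits for safety parameters will be counted" in both categories of the any-visit row. Its trigger is met in 4 of the 8 patterns, those with both a low and a high value after baseline. It is written for high and low values, and whether it extends to changes is arguable. If it did, a low-baseline subject with low and high values would also be 'to low', which the by-visit rule does not allow. The other 4 patterns are not touched.

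**The information is visible elsewhere.** This stands. The high or low value is counted in Tables 3.28 and 3.32 and listed in Listings 24 and 25. Figures 3.1 to 3.8 plot post-baseline maxima and minima against baseline, and the changes to them. A crossing at a scheduled visit also appears in that visit's row.

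**Three stronger inferences are not supported.**
- *The row percentages must sum to less than 100%.* On the complement reading nobody is omitted. On either reading a subject can count in both 'to low' and 'to high', which pushes the sum the other way.
- *All 33 analytes in protocol Table 6 (20 chemistry, 13 haematology) are affected.* An opposite-direction shift needs both a lower and an upper limit. The documents do not give the ranges, and the separate figure titles for parameters with an upper and with a lower limit suggest that some analytes have only one.
- *The largest changes are the ones lost.* A move from just below to just above a range can be smaller than a move from normal to several times the upper limit.

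**Conclusion.** The rule is wrong as written: in SAP 10.6.3 the any-visit change row does not count opposite-direction shifts that the by-visit rule counts, on either reading of the residual sentence. No other section repairs this.

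The size is small. It is confined to the safety shift summaries, Tables 3.29 and 3.33 in their overall and China versions. It touches no efficacy analysis or hypothesis test. It applies only to analytes with two-sided ranges. The documents give no frequency for such crossings; they are probably uncommon, but that is an assumption.

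The comparison between rows assumes that the tables present by-visit and any-visit rows together, as the two definitions imply. The table shells are taken from another study and are not in the documents.

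**What to change.** Replace the any-visit change rule in SAP 10.6.3 with one that follows the by-visit logic:

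- 'to high': any qualifying post-baseline value above range when baseline was not high (low or normal);
- 'to low': any qualifying post-baseline value below range when baseline was not low (normal or high);
- 'to normal or no change': all other subjects with a baseline and at least one qualifying post-baseline value.

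'Qualifying' keeps the present definition: scheduled, unscheduled or EW visits after the start of treatment, up to two weeks after the last dose. State that a subject may count in both 'to low' and 'to high'; under this rule that can happen only from a normal baseline. The baseline and post-baseline requirement largely restates SAP 10.5.2.2 and 10.7.1, but it makes the denominator explicit.

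If the normal-baseline restriction is intended, the SAP should say so and state where opposite-direction shifts are counted.

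The cost is about one sentence of SAP text and a small change to one derivation. No additional data are needed.

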11.3. Appendix 3: 12-Lead ECG Withdrawal Criteria

An ECG finding that would result in subject withdrawal post-randomization is defined as a 12-lead tracing that is interpreted as, but not limited to, any of the following:

- Sinus tachycardia ≥ 120 bpm

*Note: sinus tachycardia ≥ 120 bpm should be confirmed by two additional readings at least 5 minutes apart

- Sinus bradycardia < 37 bpm

*Note: Sinus bradycardia < 37 bpm should be confirmed by two additional readings at least 5 minutes apart.

- Increase in heart rate ≥ 40 bpm relative to baseline

*Note: increase in heart rate ≥ 40 bpm should be confirmed by two additional readings at least 5 minutes apart

- Multifocal atrial tachycardia

- Supraventricular tachycardia (> 100 bpm)

- Atrial fibrillation with rapid ventricular response (rate > 120 bpm)

- Atrial flutter with rapid ventricular response (rate > 120 bpm)

- Ventricular tachycardias (non sustained, sustained, polymorphic, or monomorphic)

- Ventricular flutter

- Ventricular fibrillation

- Torsades de Pointes

- Evidence of Mobitz type II second degree or third degree atrioventricular (AV) block

- AV dissociation

- Trifascicular Block

- An increase in QTcF > 60 msec from baseline ECG

[figure not shown]
- Uncorrected QT > 600 msec

- For subjects **with QRS duration < 120 ms**: QTc(F) ≥ 500 msec or an ECG that is unsuitable for QT measurements (e.g., poor defined termination of the T wave).

[figure not shown]
- For subjects **with QRS duration > 120 ms**: QTc(F) ≥ 530 msec or an ECG that is unsuitable for QT measurements (e.g., poor defined termination of the T wave).

- Myocardial infarction (acute or recent) Note: Evidence of an old (resolved) myocardial infarction is not exclusionary

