10.8.3. Vital Signs

Clinical concern ranges will not be used.

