| IMCT No. | China Subgroup No. | Population | IDSL / TST ID / Example Shell | Title | Programming Notes | Deliverable [Priority] |
| 3.31. | 3.31 | Modified ITT | DB2114634 7.27 | Summary of Change from Baseline in Haematology Data | | SAC |
| 3.32. | 3.32 | Modified ITT | DB2114634 7.28 | Summary of Haematology Data Outside the Normal Range | | SAC |
| 3.33. | 3.33 | Modified ITT | DB2114634 7.29 | Summary of Haematology Changes from Baseline Relative to the Normal Range | | SAC |
| 3.34. | 3.34 | Modified ITT | HZC113684 7.27 | Summary of Urinalysis Data | | SAC |
| 3.35. | 3.35 | Modified ITT | DB2114634 7.30 | Summary of Vital Signs | | SAC |
| 3.36. | 3.36 | Modified ITT | DB2114634 7.31 | Summary of Change from Baseline in Vital Signs | | SAC |
| 3.37. | 3.37 | Modified ITT | DB2114634 7.32 | Statistical Analysis of Pulse Rate (bpm) | | SAC |
| 3.38. | 3.38 | Modified ITT | DB2114634 7.33 | Statistical Analysis of Systolic Blood Pressure (mmHg) | | SAC |
| 3.39. | 3.39 | Modified ITT | DB2114634 7.34 | Statistical Analysis of Diastolic Blood Pressure (mmHg) | | SAC |
| 3.40. | 3.40 | Modified ITT | DB2114634 7.35 | Summary of ECG Values | | SAC |
| 3.41. | 3.41 | Modified ITT | DB2114634 7.36 | Summary of Change from Baseline in ECG Values | | SAC |

| Safety : Tables | | | | | | |
|-----------------|--------------------|--------------|-------------------------------|---|-------------------|------------------------|
| IMCT No. | China Subgroup No. | Population | IDSL / TST ID / Example Shell | Title | Programming Notes | Deliverable [Priority] |
| 3.42. | 3.42 | Modified ITT | DB2114634 7.37 | Summary of QTc(F) (msec) Categories | | SAC |
| 3.43. | 3.43 | Modified ITT | DB2114634 7.38 | Summary of Change From Baseline in QTc(F) (msec) Categories | | SAC |
| 3.44. | 3.44 | Modified ITT | DB2114634 7.39 | Statistical Analysis of QTc(F) (msec) | | SAC |
| 3.45. | 3.45 | Modified ITT | DB2114634 7.40 | Statistical Analysis of PR Interval (msec) | | SAC |
| 3.46. | 3.46 | Modified ITT | DB2114634 7.41 | Statistical Analysis of ECG Heart Rate (bpm) | | SAC |
| 3.47. | 3.47 | Modified ITT | DB2114634 7.42 | Summary of ECG Result Interpretations | | SAC |
| 3.48. | 3.48 | Modified ITT | DB2114634 7.44 | Summary of All ECG Abnormalities | | SAC |

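### Worst-case vital signs and ECG heart rate are derived in one direction only, so a diastolic rise or a low rate at an unscheduled or standalone Early Withdrawal visit reaches no numeric summary

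*SAP*

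**What the plan says.** **Derivation of the extremes.** SAP 10.6.3 (Vital Signs) sets one post-baseline extreme per measure: the "value will be the maximum value for pulse rate and systolic blood pressure, or the minimum value for diastolic blood pressure". Under 12-Lead ECG, the QTc(F), QTc(B), "PR interval and heart rate value will be derived as the maximum value recorded at any scheduled, unscheduled or EW visit". The SAP nowhere derives a maximum diastolic pressure, or a minimum pulse or heart rate.

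**Which readings reach the tables.** SAP 10.5.3 keeps unscheduled visits out of summary tables unless they contribute to a worst-case post-baseline assessment. SAP 10.7.1 applies the same rule to data from a standalone Early Withdrawal visit. If a subject withdraws at a scheduled visit, data from that visit's scheduled procedures are used as normal. SAP 8.3.2 analyses pulse, both pressures and heart rate by ANCOVA at scheduled time points. On threshold summaries, 10.8.3 (vital signs) states "Clinical concern ranges will not be used", and 10.8.2 says the same for ECG.

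**Which directions the plan cares about.** The cardiovascular special-interest subgroups in SAP 10.6.3 read "Cardiac Arrhythmia Cardiac Failure Cardiac Ischaemia Hypertension Stroke". Protocol Appendix 3 lists "Sinus bradycardia" among the ECG findings that lead to withdrawal.

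**Other ECG handling.** SAP 10.6.3 adds: "An 'any time post-baseline' ECG interpretation will be derived as the worst interpretation recorded at a scheduled, unscheduled or EW visit". It also says that any ECG abnormality after the start of treatment "will be included in an 'any-time post-baseline' record of all ECG abnormalities". The matching displays are Table 3.47 (result interpretations) and Table 3.48, "Summary of All ECG Abnormalities".

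**The concern.** A worst-case value should show the largest excursion in each direction that could be harmful. Here diastolic pressure is followed only downwards, while systolic pressure is followed only upwards and Hypertension is a subgroup of special interest. One component of blood pressure is therefore tracked away from the harm that the plan names. Pulse and heart rate are followed only upwards, although a low rate on ECG is a withdrawal finding.

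This is more than a display preference because, for two kinds of visit, the worst-case value is the only way into the tables. The Early Withdrawal visit requires vital signs and an ECG (Protocol 4.8), so those readings are collected by design and then summarised in one direction only. What is at stake is the completeness of the numeric safety tables; no efficacy result is affected.

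**Working it through.** The plan gives no figure to reproduce. The check sets the rules side by side and then bounds how many subjects they can affect.

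**Step 1: which direction is missing, and what else could carry the reading.** The last column refers to a reading taken at an unscheduled or standalone Early Withdrawal visit.

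| Measure | Extreme derived | Not derived | Remaining routes |
|---|---|---|---|
| Diastolic pressure | minimum | maximum | AE if judged clinically significant; Listing 48 |
| Systolic pressure | maximum | minimum | AE if judged clinically significant; Listing 48 |
| Pulse rate | maximum | minimum | AE if judged clinically significant; Listing 48 |
| ECG heart rate | maximum | minimum | Tables 3.47 and 3.48 if recorded as an abnormality; AE; Listings 49 and 50 if any ECG is read as abnormal |

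**Step 2: can the derived extreme respond to the missing direction?** Let d1, ..., dk be a subject's other post-baseline diastolic readings and x the reading at the unscheduled or Early Withdrawal visit. Then min(d1, ..., dk, x) = min(d1, ..., dk) whenever x is at or above the lowest of the others. A rise therefore leaves the minimum unchanged, whatever its size. In the same way max(h1, ..., hk, x) = max(h1, ..., hk) whenever x is at or below the highest of the others, so a low rate leaves the maximum unchanged. The one exception is a subject whose only post-baseline reading is x, because the minimum and maximum then coincide.

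**Step 3: is there another numeric route?** The by-visit summaries exclude these visits (10.5.3, 10.7.1), the ANCOVA uses scheduled time points (8.3.2), and there are no threshold counts (10.8.2, 10.8.3). No numeric route remains.

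**Step 4: compare with the laboratory rule.** In the same section, laboratory values are classed low or high at any scheduled, unscheduled or Early Withdrawal visit. SAP 10.6.1 counts a subject with both high and low values for a safety parameter in both categories. The SAP thus already works in both directions for laboratory data, and it gives no reason for doing otherwise with vital signs and heart rate.

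**Step 5: upper bound on subjects affected through Early Withdrawal.** Inputs are 288 randomised, 192 to UMEC and 96 to placebo, and 18% expected to withdraw without a Week 24 assessment (Protocol 8.2.1).

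- Overall: 0.18 × 288 = 51.8, about 52.
- By arm, assuming equal rates: 0.18 × 192 = 34.6, about 35; 0.18 × 96 = 17.3, about 17.

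This is a ceiling on standalone Early Withdrawal visits at the planned rate. It includes subjects who withdraw at a scheduled visit, whose scheduled vital signs are kept, and subjects lost to follow-up, who have no such visit. The documents give no number for unscheduled visits, so that part cannot be bounded.

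**The case against.** The strongest reply is that the gap is narrow and that other routes carry the important events.

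- **Bradycardia.** A reader might infer that bradycardia appears in no worst-case summary. The documents do not support that. The withdrawal criterion concerns an interpreted ECG tracing, and ECG findings are carried into the any-time interpretation and the any-time abnormality record without limit on direction. What stands is that the low rate has no numeric summary, and that a low pulse at an unscheduled visit without an ECG is outside this route.
- **Adverse events.** Protocol 6.3.5.1 counts vital-sign and ECG results as AEs when the investigator finds them clinically significant, whatever the visit. Such events reach the AE tables, including Table 3.20 for those leading to withdrawal and Table 3.21 for on-treatment events of special interest. This stands, but it depends on individual judgement, whereas a derived extreme does not.
- **Scheduled data.** Diastolic rises at scheduled visits, including the post-dose readings on Day 1, enter the by-visit summaries and models. Those summaries may also show minima and maxima: SAP 10.5.3 refers to an external reporting standard that is not reproduced.
- **Choice of direction.** The risk table in Protocol 1.3 names atrial fibrillation and tachycardia, so a maximum for pulse and heart rate fits the named risk. This explains why the maximum is there, but not why the minimum is absent. It does not explain the choice for diastolic pressure.
- **Timing of reactions.** One might suppose that unscheduled and Early Withdrawal visits are where a cardiovascular reaction is most likely to be measured. No passage says so, and the Early Withdrawal visit follows discontinuation of study drug. The point does not need that premise.

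**Conclusion.** The point holds as a limited reporting gap. No maximum diastolic pressure and no minimum pulse or ECG heart rate is derived. A diastolic rise or a low rate measured at an unscheduled or standalone Early Withdrawal visit therefore reaches no numeric summary, apart from the single-reading exception above. A diastolic rise has no worst-case display at all; ECG-recorded bradycardia has a categorical one.

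The Early Withdrawal part concerns at most about 52 subjects at the planned withdrawal rate, and probably fewer. The unscheduled part is of unknown size. Safety reporting as a whole is not blind to these events, since the AE tables, the ECG tables and the listings remain.

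Two assumptions apply. That a diastolic rise matters to this plan is inferred from the Hypertension subgroup, because no passage names it as a risk. That the worst-case rows sit in the vital-sign and ECG value tables is also inferred, because the table shells come from a reference study and are not shown.

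**What to change.** In SAP 10.6.3, derive both the maximum and the minimum post-baseline value, and the change from baseline to each, for diastolic pressure, systolic pressure, pulse rate and ECG heart rate, over scheduled, unscheduled and Early Withdrawal visits. Show both rows in Tables 3.35 and 3.36 (vital signs) and in Tables 3.40 and 3.41 (ECG values). Make the change before unblinding.

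The data are already collected, and no clinical threshold or withdrawal rule changes. The cost is a few extra rows in four existing tables, which become slightly longer and no longer match the reference-study shells exactly.
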